8.12 Physical Examinations

A full physical examination will be performed at the Screening Visit, the EOT Visit, and Day 60. A full physical examination may include assessments of general condition, skin,

eyes/ears/nose/mouth/throat, neck/thyroid, chest/lungs, heart, vascular system, lymph nodes, abdomen, extremities, nervous systems/reflexes, musculoskeletal system, and spine.

A brief physical examination or a telemedicine-based physical examination (if the patient and site have video capabilities) will be performed at the other visits as indicated in Appendix A. For inpatients, a brief physical examination, targeted to patient symptoms, will be performed at the other visits. For outpatients, telemedicine-based physical examinations will be performed at the other visits (if the patient and site have video capabilities). Telemedicine-based physical examinations may include assessments of general condition (eg, overall appearance and patient orientation) and an assessment of the work of breathing (eg, speech cadence, lifting hands above head). If the patient or the site do not have video capabilities, the video portion of the telemedicine-based physical examination will be omitted, and the visit will be performed by phone. In this case and in lieu of the physical or video examination, clinicians will document whether the patient is having audible shortness of breath or difficulty speaking. If there are any concerns, then the patient will be instructed to call to his/her local physician or be seen at his/her local emergency department.

9 STATISTICS

9.1 Analysis Populations

The following analysis populations are defined for this study:

Intent-to-Treat (ITT) Population: The ITT Population is defined as all randomized patients. The ITT Population will be the primary population for analysis of efficacy data. Efficacy analyses will be based on the assigned treatment group.

Safety Population: The Safety Population is defined as all randomized patients who receive at least 1 dose of study drug. All safety data will be analyzed using the Safety Population. Safety analyses will be based on the treatment actually received.

Per-Protocol (PP) Population: The PP Population is defined as all patients in the ITT Population who complete the study with no major protocol deviations that may impact the primary efficacy assessment. The primary analysis will be repeated on the PP Population. Major protocol deviations will include violations of key entry criteria or deviations that could significantly impact the assessment or interpretation of efficacy data.

PK Population: The PK Population is defined as all patients with at least 1 PK measurement drawn during the study.

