Per-Protocol (PP) Population: The PP Population is defined as all patients in the ITT Population who complete the study with no major protocol deviations that may impact the primary efficacy assessment. The primary analysis will be repeated on the PP Population. Major protocol deviations will include violations of key entry criteria or deviations that could significantly impact the assessment or interpretation of efficacy data.

PK Population: The PK Population is defined as all patients with at least 1 PK measurement drawn during the study.

Patients who discontinue the study drug will remain in the study to have safety and efficacy assessments performed. Patients should be encouraged to follow-up for key study visits (Day 28 and Day 60) but will not be required to attend every study visit. The data observed on-study will be used for analysis regardless of any intercurrent events. Patients who die or discontinue treatment prior to the assessment time point (Day 28 or Day 60) because of lack of efficacy, and cannot have clinical status determined at the time point, will be considered treatment failures. Details regarding data handling and imputation method will be provided in the Statistical Analysis Plan (SAP).

The primary efficacy endpoint is the proportion of patients alive and not requiring non-invasive or invasive ventilation (ie, not receiving high-flow nasal cannula, non-invasive positive pressure ventilation, invasive mechanical ventilation, or ECMO) at Day 28. The treatment group difference of the response proportions, along with the corresponding 95% confidence interval and p-value, will be provided using the logistic regression model by Guo et al. (2012) and Ge et al. (2011), adjusted for stratification factor (use of invasive mechanical ventilation at the time of randomization [yes or no]). Additional prognostic baseline covariates (eg, age, region, body mass index) may be added as covariates/factors into the model to increase precision in the estimation of difference in proportions. Details will be provided in the SAP.

The primary analysis will be repeated on the PP Population.

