3 STUDY DESCRIPTION

3.1 Summary of Study Design

This is a Phase 2/3, randomized, double-blind, placebo-controlled, multicenter study to evaluate the efficacy and safety of FP-025 in adult patients with severe to critical COVID-19 with associated ARDS. The patients in each phase (Phase 2 and Phase 3) will be analyzed separately.

Each phase will consist of a Screening Visit, Treatment Period, and Follow-Up Period for a total study duration of approximately 60 days.

3.1.1 Phase 2

After eligibility is confirmed, approximately 99 patients will be randomized in a 1:1:1 ratio to receive FP-025 100 mg BID, FP-025 300 mg BID, or placebo BID for 28 days. During Phase 2, randomized patients will be stratified by the use of invasive mechanical ventilation at the time of randomization (yes or no). At least one-third of patients should be on invasive mechanical ventilation to ensure that treatment benefits can be assessed for patients at different severity levels.

Patients with Grade 3 to Grade 4 heart failure, Stage 3 or greater COPD, persistent asthma, and mild liver disease (ie, Child-Pugh Class A) will not be excluded from the study. The independent Data Monitoring Committee (iDMC) will independently monitor safety of the entire population and in different subgroups and may make recommendations as it deems appropriate. During Phase 2, no limitation in enrollment of subgroups is expected, unless clear safety signals arise in those subgroups during iDMC reviews.

The reason for hospital admission, the standard of care followed for each patient and center, and whether any care decisions were based on resource limitations will be clearly documented for all patients beginning on Day 1 (Visit 2). All patients will be allowed to receive standard of care and/or emergency use authorization (EUA) medications and treatment for COVID-19; however, the study drug should be discontinued for other non-standard of care concomitant medications used with the intent of directly treating COVID-19 unless there is prior Medical Monitor or Sponsor approval for the patient to remain on the study drug. If the use of concomitant medications necessitates study drug discontinuation, the patient should be encouraged to remain in the study and to follow-up for key study visits (Day 28 and Day 60) but will not be required to attend every study visit. If the patient withdraws, he/she should complete the Early Termination Visit.

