7.1.2 Key Secondary Efficacy Endpoints

The key secondary efficacy endpoints include the following, with each dose (Phase 2) or the optimal dose (Phase 3) of FP-025 compared to placebo:

- Proportion of patients on invasive mechanical ventilation at Day 28;
- Proportion of patients alive at Day 28;
- Proportion of patients alive and not requiring non-invasive or invasive ventilation (ie, not receiving high-flow nasal cannula, non-invasive positive pressure ventilation, invasive mechanical ventilation, or ECMO) at Day 60;
- Proportion of patients on invasive mechanical ventilation at Day 60; and
- Proportion of patients alive at Day 60.

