8 SAFETY ASSESSMENTS

8.1 Adverse Events

An AE is defined as any untoward medical occurrence in a clinical investigation patient administered a pharmaceutical product, which does not necessarily have a causal relationship with this treatment. An AE can therefore be any unfavorable and/or unintended sign (including an abnormal laboratory finding), symptom, or disease temporally associated with the use of an investigational medicinal product, whether or not related to the investigational medicinal product. All AEs, including observed or volunteered problems, complaints, or symptoms, are to be recorded on the appropriate eCRF.

AEs will be monitored and recorded from the time of the first dose of study drug (Day 1 [Visit 2]) until the end of the study (Day 60). All events occurring prior to the first dose of study drug will be recorded as medical history. Patients should be instructed to report any AE that they experience to the Investigator, whether or not they think the event is due to study treatment. Beginning at Day 1 (Visit 2), Investigators should make an assessment for AEs at each visit and record the event on the appropriate AE eCRF.

Wherever possible, a specific disease or syndrome rather than individual associated signs and symptoms should be identified by the Investigator and recorded on the eCRF. However, if an observed or reported sign or symptom is not considered a component of a specific disease or syndrome by the Investigator, it should be recorded as a separate AE on the eCRF. Additionally, the condition that led to a medical or surgical procedure (eg, surgery, endoscopy, tooth extraction, or transfusion) should be recorded as an AE, not the procedure itself.

Any medical condition already present prior to the first dose of study drug should be recorded as medical history and not be reported as an AE unless the medical condition or signs or symptoms present at baseline changes in severity, frequency, or seriousness at any time during the study. In this case, it should be reported as an AE.

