9.2 Statistical Methods

9.2.1 Analysis of Efficacy

Patients who discontinue the study drug will remain in the study to have safety and efficacy assessments performed. Patients should be encouraged to follow-up for key study visits (Day 28 and Day 60) but will not be required to attend every study visit. The data observed on-study will be used for analysis regardless of any intercurrent events. Patients who die or discontinue treatment prior to the assessment time point (Day 28 or Day 60) because of lack of efficacy, and cannot have clinical status determined at the time point, will be considered treatment failures. Details regarding data handling and imputation method will be provided in the Statistical Analysis Plan (SAP).

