9.2.1.1 Primary efficacy analysis

The primary efficacy endpoint is the proportion of patients alive and not requiring non-invasive or invasive ventilation (ie, not receiving high-flow nasal cannula, non-invasive positive pressure ventilation, invasive mechanical ventilation, or ECMO) at Day 28. The treatment group difference of the response proportions, along with the corresponding 95% confidence interval and p-value, will be provided using the logistic regression model by Guo et al. (2012)²⁴ and Ge et al. (2011),²⁵ adjusted for stratification factor (use of invasive mechanical ventilation at the time of randomization [yes or no]). Additional prognostic baseline covariates (eg, age, region, body mass index) may be added as covariates/factors into the model to increase precision in the estimation of difference in proportions. Details will be provided in the SAP.

The primary analysis will be repeated on the PP Population.

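### The Per-Protocol set requires completion of a 60-day study, so the repeat of the Day 28 primary analysis drops patients who die, and death is one of its failure events

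*Combined protocol and SAP*

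**What the plan says.** Section 9.1 gives the PP definition as "all patients in the ITT Population who complete the study with no major protocol deviations that may impact the primary efficacy assessment". The Synopsis, under Statistical Analyses, has the same rule: "The PP Population is defined as all patients in the ITT Population who complete the study with no major protocol deviations". Section 9.2.1.1 then states: "The primary analysis will be repeated on the PP Population".

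That primary analysis concerns a Day 28 endpoint: alive and receiving none of high-flow nasal cannula, non-invasive ventilation, invasive ventilation or ECMO. A death by Day 28 is therefore a non-response.

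The study continues past Day 28. Section 3.1 describes a "Follow-Up Period for a total study duration of approximately 60 days", and Section 8.1 also places the end of the study at Day 60. The one explicit definition of study completion, in Section 10.3, is for the whole trial (last visit of the last patient) and not for an individual.

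For efficacy in general, Section 9.2.1 says: "The data observed on-study will be used for analysis regardless of any intercurrent events". It also classes certain deaths and discontinuations before the time point as treatment failures. On the standing of the PP set, Section 9.1 is clear: "The ITT Population will be the primary population for analysis of efficacy data".

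**The concern.** The definition sets two conditions: the patient completes the study, and has no major deviation that matters for the primary assessment. The second is what a PP set is for. The first is a post-randomization event tied to the outcome. A patient who dies on Day 10 does not complete a 60-day study and is removed, so the most severe failures leave the analysis. A patient whose Day 28 status is known and who withdraws on Day 40 is removed as well, although nothing about the Day 28 assessment is in doubt.

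A PP repeat normally shows whether protocol deviations drive the ITT result. Here the two analyses can differ because deaths were removed, so a difference from ITT, or agreement with it, cannot be put down to deviations alone. A drug that prevents deaths can look weaker in the PP set, and one with excess deaths can look better.

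There is also a timing difficulty. Under Section 9.2.3 the Phase 2 primary analysis takes place when all patients have reached Day 28. Day 60 completion is then unknown for the most recent enrollees. If the PP repeat accompanies that analysis, membership cannot be settled for them.

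**Working it through.** **The plan's own figure.** Section 9.2.5 plans 60% versus 75% response, 1-sided 0.025, 304 patients (152 per arm), about 80% power. The pooled two-proportion formula gives

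n = [1.960·√(2·0.675·0.325) + 0.8416·√(0.60·0.40 + 0.75·0.25)]² / 0.15² = 151.9, so 152 per arm.

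Power at 152 per arm is 0.800. The plan's figure reproduces, and 60%/75% with 152 per arm is used below.

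**Effect of removing deaths.** Let p be the Day 28 response in an arm and m the mortality by Day 28. Every such death is a non-responder, so removing deaths leaves the responders unchanged and shrinks the denominator:

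PP response = p / (1 − m); patients removed = 152 × (m control + m drug).

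Mortality by arm is not in the documents and is assumed here. The planned response rates cap it at 40% for control (1 − 0.60) and 25% for drug (1 − 0.75). Section 1.1 cites death rates of at least 50% in COVID-19 ARDS, so deaths should not be rare.

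| Assumed mortality, control / drug | PP response, control / drug | PP difference (ITT = 15.0) | Removed of 304 |
|---|---|---|---|
| 40% / 25% (every failure a death) | 100% / 100% | 0 | 99 |
| 35% / 20% | 92.3% / 93.75% | 1.4 | 84 |
| 25% / 12% | 80.0% / 85.2% | 5.2 | 56 |
| 20% / 10% | 75.0% / 83.3% | 8.3 | 46 |
| 20% / 12.5% (half of failures in each arm) | 75.0% / 85.7% | 10.7 | 49 |
| 10% / 10% | 66.7% / 83.3% | 16.7 | 30 |
| 15% / 15% | 70.6% / 88.2% | 17.6 | 46 |
| 20% / 20% | 75.0% / 93.75% | 18.75 | 61 |

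The direction is not fixed. With 20% control mortality, the PP difference equals 15 points when 0.75/(1 − m) = 0.90, that is at m = 16.7% on drug. Lower drug mortality gives a smaller PP difference and higher drug mortality a larger one.

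**No effect on the endpoint.** Take 60% response in both arms, so the ITT difference is 0.
- Mortality 25% control, 15% drug: 0.60/0.85 − 0.60/0.75 = 70.6% − 80.0% = −9.4 points.
- Mortality 15% control, 25% drug: +9.4 points.

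**Patients who leave after Day 28 with known status.**
- If leaving is unrelated to outcome and arm, the difference stays at 15 points. Losing 5% or 10% lowers the power of the PP analysis to 0.780 or 0.757.
- If only responders leave, at rate d in both arms, the PP response is p(1 − d) / [p(1 − d) + 1 − p]. For d = 5% this gives 58.8% versus 74.0%, difference 15.3. For d = 20% it gives 54.5% versus 70.6%, difference 16.0.

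This part is mainly a loss of precision. Removal of deaths is the main problem.

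**Does another section put these patients back?**
- Section 9.2.1 (deaths as failures) sets the outcome of patients who are analysed. It does not decide who is in the PP set.
- Section 9.2.3 uses completed and discontinued together, but only for the timing of the final analysis.
- Section 4.4 lists consent withdrawal or patient request, and loss to follow-up, as reasons for ending participation. It does not say that a patient who dies has completed.
- Section 10.3 is at trial level.

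None of them restores the patients removed.

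**The case against.** The strongest reply is that exclusion of deaths is an inference. Completion is undefined for a patient, Section 4.4 does not list death as a discontinuation, and someone followed until death could be said to have completed all possible follow-up. Table 1 in Section 9.2.3 even has a completers column, with a footnote that covers patients who reach the Day 28 visit or stop early but would have reached it. This does not rescue the definition. The footnote counts patients for the interim and final boundaries and includes early discontinuations, so it cannot be the PP rule. No section calls a death a completion. Even if one did, withdrawals and losses after Day 28 would still be removed.

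Three points on the other side do stand.
- The figures depend on assumed mortality, and some pairs are stretched. At 20% in both arms, deaths are half of control failures (20/40) but 80% of drug failures (20/25). The formula also covers only deaths by Day 28, not those between Day 28 and Day 60.
- A table of PP exclusions by reason and arm would let a reader see part of what drove a discrepancy, so the repeat would not be wholly uninterpretable.
- The reach is small. No decision rule uses the PP set, it is outside the hierarchy in Section 9.2.1.3, survival is tested in its own right ("Proportion of patients alive at Day 28", Section 7.1.2), and the named sensitivity analysis is the tipping point method.

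Sections 9.2.1 and 9.2.1.1 defer details to the SAP, and no separate SAP text on the PP set was available. What they defer is data handling, imputation and model detail. The PP definition itself is given in full in Section 9.1.

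**Conclusion.** The concern holds. Followed as written, the PP definition conditions a Day 28 analysis on an event up to Day 60 that excludes deaths, and so selects on outcome. Across the assumed mortality pairs, a planned 15-point difference becomes anything from 0 to 18.75 points, and a null effect can appear as 9.4 points in either direction. These sizes rest on assumed mortality by arm, on all deaths by Day 28 being removed, and on there being no other PP exclusions. That the rule selects on outcome rests only on the plain reading of Section 9.1. The consequence is limited to a supportive analysis, which makes this worth correcting but no threat to the trial's main conclusion.

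**What to change.** Replace the definition in Section 9.1 and the Synopsis, and match it in the SAP, with a sentence such as:

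> The PP Population consists of ITT patients without a major protocol deviation up to Day 28 that could affect the primary assessment; neither death nor failure to complete follow-up after Day 28 is a reason for exclusion, and deaths by Day 28 count as non-responders, as in the ITT analysis.

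The SAP should also say how a patient who leaves alive before Day 28 with unknown status is treated. With deaths kept and no other exclusions, the PP comparison returns to the primary one: 60% versus 75%, 15.0 points, 152 per arm, power 0.800. The actual PP number will depend on major deviations, which the plan does not forecast.

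The cost is one sentence in each place, with no new data and no change to the sample size or the primary test. It should be settled before the Phase 2 primary analysis, because choosing the reading after unblinding would be a data-dependent decision.

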9.2 Statistical Methods

9.2.1 Analysis of Efficacy

Patients who discontinue the study drug will remain in the study to have safety and efficacy assessments performed. Patients should be encouraged to follow-up for key study visits (Day 28 and Day 60) but will not be required to attend every study visit. The data observed on-study will be used for analysis regardless of any intercurrent events. Patients who die or discontinue treatment prior to the assessment time point (Day 28 or Day 60) because of lack of efficacy, and cannot have clinical status determined at the time point, will be considered treatment failures. Details regarding data handling and imputation method will be provided in the Statistical Analysis Plan (SAP).

9.2.1.1 Primary efficacy analysis

The primary efficacy endpoint is the proportion of patients alive and not requiring non-invasive or invasive ventilation (ie, not receiving high-flow nasal cannula, non-invasive positive pressure ventilation, invasive mechanical ventilation, or ECMO) at Day 28. The treatment group difference of the response proportions, along with the corresponding 95% confidence interval and p-value, will be provided using the logistic regression model by Guo et al. (2012)²⁴ and Ge et al. (2011),²⁵ adjusted for stratification factor (use of invasive mechanical ventilation at the time of randomization [yes or no]). Additional prognostic baseline covariates (eg, age, region, body mass index) may be added as covariates/factors into the model to increase precision in the estimation of difference in proportions. Details will be provided in the SAP.

The primary analysis will be repeated on the PP Population.

9.2.1.2 Secondary efficacy analysis

The key secondary endpoints of the proportion of patients alive and not requiring non-invasive or invasive ventilation (ie, not receiving high-flow nasal cannula, non-invasive positive pressure

ventilation, invasive mechanical ventilation, or ECMO) at Day 60, the proportion of patients on invasive mechanical ventilation at Day 28 and at Day 60, and the proportion of patients alive at Day 28 and Day 60, will be analyzed using the same method as for the primary analysis.

Tipping point method will be used as a sensitivity analysis for evaluating the robustness of the results for the primary endpoint and key secondary endpoints.

Other secondary endpoints will be analyzed as described in the SAP. For all endpoints defined by events, the time points are defined as the number of days after randomization.

The Phase 2 study is not powered. No alpha controlling strategy will be implemented.

9.2.1.3 Multiplicity in Phase 3

To control the overall Type I error in the final analysis for Phase 3, a fixed sequential testing procedure will be implemented. In a hierarchical step-down manner, the primary efficacy endpoint will be tested at the 1-sided 0.025 level first, followed by testing the secondary efficacy endpoints at the 1-sided 0.025 level in the following hierarchical manner: (1) proportion of patients on invasive mechanical ventilation at Day 28, (2) proportion of patients alive at Day 28, (3) proportion of patients alive and not requiring non-invasive or invasive ventilation (ie, not receiving high-flow nasal cannula, non-invasive positive pressure ventilation, invasive mechanical ventilation, or ECMO) at Day 60, (4) proportion of patients on invasive mechanical ventilation at Day 60, and (5) proportion of patients alive at Day 60.

Inferential conclusions about these efficacy endpoints will require statistical significance of the previous endpoints and the primary efficacy endpoint.

This is not applicable to Phase 2 since Phase 2 is not powered.

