An iDMC will convene to oversee safety and efficacy assessments during and after the Phase 2 study. The first iDMC meeting will occur after approximately 10 to 15 patients have been enrolled. The second iDMC meeting will occur after approximately 50% to 60% of patients have been enrolled. No formal statistical testing will be conducted. In addition, when all patients in the Phase 2 study have completed the EOT Visit on Day 28, a primary analysis will be conducted by an independent statistician and reviewed by the iDMC.

3.1.2 Phase 3

Based on the results of the primary analysis of Phase 2, 1 optimal dose will be selected to carry into Phase 3. Once the optimal dose has been selected, the study may proceed to Phase 3. Patients will be randomized in a 1:1 ratio to receive FP-025 or placebo for 28 days. Similar procedures will be followed as for Phase 2; however, study design (eg, eligibility criteria, sample size number, protocol-defined procedures, and timing of procedures) or dosing may be changed based on iDMC recommendations after data from the primary analysis in Phase 2 becomes available. If the iDMC recommends modification of the protocol, and the Sponsor is in agreement, the protocol will be amended and submitted to regulatory authorities and Institutional Review Boards (IRBs) for approval. An interim analysis will be conducted after approximately 70% (213 out of 304) of the randomized patients have completed the EOT Visit on Day 28 or have discontinued early, but would have reached Day 28 had they remained in the study, to assess for safety, early futility, and potential sample size recalculation.

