Planned Analysis	Total Completers [1]	Information Fraction	Futility Boundary		Boundary Crossing Probability (Incremental)		Cumulative Beta Spent
			Z Scale	Nominal P-Value	Under H_0	Under H_1	
Interim	213	0.7	0.789	0.2151	0.785	0.057	0.0572
Final	304	1	1.960	0.025	0.191	0.141	0.198

1. Patients who complete the Day 28 visit or discontinue early, but would have reached Day 28.

Futility testing (Phase 3)

The process is as follows:

- Futility at the interim analysis: If the 1-sided p-value is ≥ 0.2151 (or the observed z-statistic is ≤ 0.789), then the futility boundary is crossed and the null hypothesis will be accepted; and
- At the final analysis: The final hypothesis is tested at the 1-sided significance level of 0.025.

In case the number of patients at the interim analyses are not exactly equal to the planned number of patients (ie, the first 213 patients who completed the EOT Visit on Day 28 or have discontinued early but would have reached Day 28), the futility boundary will be revised based on the actual number of patients at the interim analysis.

Sample size recalculation (Phase 3)

At the interim analysis for early futility, when the first 213 patients complete the EOT Visit on Day 28 or have discontinued early but would have reached Day 28, the iDMC will also assess for potential sample size recalculation for the study using the promising-zone method. Wald conditional probabilities will be calculated using the actual observed proportions from both treatment arms. The maximum sample size allowed is 608 patients. Sample size will be increased only if the observed data at the interim analysis are promising; that is, if the conditional power is $\geq 36\%$ and $< 80\%$, as described in the SAP.

Possible recommendations by the iDMC

After reviewing the results of the interim analysis, the iDMC may select 1 of 4 or more possible recommendations, based on the test statistics obtained at the interim analysis, as follows:

- Stop for early futility: Stop study early due to strong evidence for futility due to test statistic being in the futility region;
- Continue without change: Continue with no changes due to test statistic not being in the futility region or the conditional power being $< 36\%$ or $\geq 80\%$;
- Add required additional sample size, n, without exceeding the maximum sample size and continue the study; or
- Stop for safety concerns.

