9.2.5 Sample Size Determination

For the Phase 2 study, approximately 99 patients will be randomized in a 1:1:1 ratio to 1 of 3 treatment groups: FP-025 100 mg BID, FP-025 300 mg BID, or placebo BID. No formal statistical assessment for sample size determination has been performed. The sample size is considered adequate to provide the necessary data to evaluate the objectives of the study.

For Phase 3, a total of 304 patients (152 patients per treatment group) will provide approximately 80% power to detect a 15% improvement in response rate, based on a control response rate of 60% and assuming a response rate of 75% with the study drug treatment group, using a 1-sided 0.025 level test. The sample size estimate assumes that an interim analysis will be conducted after approximately 70% of patients (approximately 213 patients) have completed the EOT Visit on Day 28 or have discontinued early, but would have reached Day 28 had they remained in the study, to assess early futility and potential sample size recalculation. The sample size was calculated using EAST 6.4. The Phase 3 sample size will be formally recalculated based on results from the Phase 2 part of the study. A maximum of 608 patients may be included. If the iDMC, in consultation with the Sponsor determines that a sample size of more than 608 patients is needed, a protocol amendment will be required.

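### The promising-zone increase protects only the primary test, so the key secondary sequence can slightly exceed its stated one-sided 0.025

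*Combined protocol and SAP*

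**What the plan says.** Protocol 9.2.1.3 sets up a fixed sequence for Phase 3: "To control the overall Type I error in the final analysis for Phase 3, a fixed sequential testing procedure will be implemented". The primary is "tested at the 1-sided 0.025 level first, followed by testing the secondary efficacy endpoints at the 1-sided 0.025 level in the following hierarchical manner": invasive ventilation at Day 28, survival at Day 28, the composite at Day 60, invasive ventilation at Day 60, survival at Day 60. Gating is strict: "Inferential conclusions about these efficacy endpoints will require statistical significance of the previous endpoints and the primary efficacy endpoint". Under 9.2.1.2 the key secondaries "will be analyzed using the same method as for the primary analysis", a covariate-adjusted risk difference from logistic regression.

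Protocol 9.2.3 places an interim analysis at 213 patients and allows a promising-zone increase: "Sample size will be increased only if the observed data at the interim analysis are promising", meaning conditional power of at least 36% and below 80% at the observed proportions, with a cap of 608. The same section spends 0.0001 at the interim to preserve 0.025, but says this only of the primary analysis. No weighted statistic, combination test or adjusted level is given for any secondary after an increase. Details of the rule are left to the SAP.

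**The concern.** An ordinary final test survives a promising-zone increase only because patients are added when the tested endpoint's own interim result is already favourable. For the primary this holds by construction. For a secondary it does not: the decision looks at the primary, and a null secondary lacks the primary's treatment effect. In the zone its interim statistic is usually mediocre, and added patients dilute it. When the primary does very well the size stays put, so a secondary that is doing well by chance is not diluted. The increase is therefore applied selectively where it helps a false positive.

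At stake is a property the plan asserts. A claim on a key secondary from an enlarged trial could rest on an error rate slightly above the one stated.

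**Working it through.** **Inputs from the protocol.** "a total of 304 patients (152 patients per treatment group) will provide approximately 80% power to detect a 15% improvement in response rate" (9.2.5), with 60% on placebo and 75% on FP-025 assumed there; interim at n1 = 213; zone 36% to below 80%; cap 608; futility at z ≤ 0.789, non-binding (9.2.3). **Assumed:** the correlation ρ between each secondary and the primary, which the documents do not give, and the re-sizing formula. I took two versions: raise N to reach 80% conditional power (capped at 608), or go straight to 608.

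**1. Reproduce the design.** SE = √[(0.60×0.40 + 0.75×0.25)/152] = 0.0530, so the expected final z is 0.15/0.0530 = 2.83. Power is 80.0% by the pooled formula without the look, and 80.2% (unpooled) with the futility look. The futility probabilities of 0.785 under H0 and 0.057 under H1, and the total beta of 0.198, match Table 1.

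**2. The zone on the z scale.** CP(z) = Φ{[z√n1 − 1.96√N]/√(N−n1) + z√[(N−n1)/n1]} with N = 304.
- z = 1.476: (21.54 − 34.17)/9.54 + 0.965 = −0.36, giving CP 36%.
- z = 2.026: (29.57 − 34.17)/9.54 + 1.324 = 0.84, giving CP 80%.

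**3. The primary is protected.** An increase to 608 raises the conditional error of the ordinary test only if the interim z is below 1.446 (CP 33.6%). The zone starts above that. The overall primary error is 0.0238 (80% target) or 0.0225 (straight to 608).

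**4. Why this does not carry over.** Suppose the true primary effect is about 9 points, so the expected final z is 1.7 and the expected interim z is 1.7×√(213/304) = 1.42. With ρ = 0.8, a null secondary in the zone has mean interim z of 0.8×(1.476 − 1.42) to 0.8×(2.026 − 1.42), about 0.04 to 0.48. That is far below 1.446. At an interim value of 0.26, its conditional error is 0.0007 at N = 304 and 0.0125 at N = 608.

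**5. Overall error of a null secondary.** I integrated P(primary z > 1.96 and secondary z > 1.96) over the interim primary z, with only the primary gate. Without re-sizing the maximum is 0.0250 at every ρ.

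| ρ | Max, 80% target | Primary effect at that max | 15-point effect, 80% target | Max, straight to 608 |
|---|---|---|---|---|
| 0.3 | 0.0251 | 20 points | 0.0244 | 0.0253 |
| 0.45 | 0.0253 | 16 points | 0.0252 | 0.0256 |
| 0.57 | 0.0255 | 14 points | 0.0255 | 0.0260 |
| 0.7 | 0.0259 | 11 points | 0.0255 | 0.0265 |
| 0.8 | 0.0263 | 9 points | 0.0254 | 0.0271 |
| 0.9 | 0.0268 | 7 points | 0.0252 | 0.0277 |

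At 15 points the straight-to-608 rule gives at most 0.0260. Separate calculations agree to about 0.0001. Applying the futility stop changes the maxima by less than 0.0001.

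**6. Plausible correlations.** For an event with rate q that is always a primary failure, ρ = √[p/(1−p) × q/(1−q)], where p is the response rate. At p = 0.60: 0.41 for q = 10%, 0.61 for 20%, 0.80 for 30%. At p = 0.70 and q = 25%: 0.88.

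**7. Patient-level check.** With 60% vs 70.5% response and a 25% null event rate, the error is 0.0268 with the increase and 0.0255 without it, so the increase itself adds about 0.0013.

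**8. The remedy.** With fixed weights √(213/304) and √(91/304), the normal-theory error returns to 0.0248–0.0250. At patient level (same scenario), combining in every trial, where an unenlarged second stage has only 45 or 46 patients per arm, gives about 0.0265 with unpooled Wald stage-wise statistics and about 0.025 with pooled ones. Combining only in enlarged trials gives about 0.0255 with either, close to the figure without an increase.

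**The case against.** **Later gates.** A reader might infer that the Day 28 survival claim itself runs at 0.026 to 0.027. The documents do not support that, because survival must first pass invasive ventilation at Day 28. In the scenario of step 7, adding that gate gave 0.0167 with ventilation rates of 10% vs 3% and 0.0221 with 15% vs 4.5%. The value returned to 0.0268 only at 15% vs 0%, an almost maximal ventilation effect with none on death. This objection stands (the ventilation rates are assumed).

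**The first secondary.** Invasive ventilation at Day 28 has only the primary gate. If deaths do not count as events, null rates of 8–15% imply correlations of about 0.36–0.65 and simulated error of 0.021–0.025; it reached 0.0260 at 20%. That also stands. But 9.2.1 treats patients who die, and whose status cannot be determined, as treatment failures. If that rule applies here, the endpoint becomes ventilated-or-dead, with a much higher correlation.

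**Size and source.** The high figures are maxima over an unknown effect at assumed correlations, and part of the simulated excess is present without any increase. Both are correct. They limit the size of the point; they do not restore the stated control, which has to hold at every true primary effect.

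**The SAP.** The rule is deferred to it, and its text is not in the documents supplied. A weighted secondary statistic there would settle the matter, so the gap is shown for the protocol only.

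**Conclusion.** The point holds as a small loss of strict control. For a null key secondary positively correlated with an effective primary, the ordinary test after a promising-zone increase exceeds 0.025 by at most about 0.002 when N is raised to 80% conditional power, or about 0.003 when it goes straight to 608. Under the first rule the worst case is 0.026 to 0.027 at correlations of 0.7 to 0.9 and intermediate primary effects of roughly 7 to 11 points. It is at most about 0.0255 at the design effect, and there is little or no excess at correlations up to about 0.5.

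It bears most directly on invasive ventilation at Day 28, especially if deaths count as failures. It would be wrong to read 0.026 to 0.027 as the actual error of every key secondary. It would also be wrong to conclude that the primary test is affected, since its error stays below 0.025. The conclusion rests on assumed correlations, an assumed re-sizing formula, and the absence of a provision in the SAP.

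**What to change.** Add to 9.2.1.3, and carry into the SAP:
- If the sample size is increased at the interim, each key secondary is tested against 1.96 with w1·Z1 + w2·Z2, or an equivalent conditional-error test.
- The weights are w1 = √(interim n / planned N) and w2 = √(1 − interim n / planned N). On current figures these are √(213/304) and √(91/304). Define them by the planned fraction, because 9.2.3 and 9.2.5 provide for recalculating the Phase 3 size from Phase 2 results.
- Z1 uses the patients in the interim data set, each followed to their own Day 28 or Day 60. Z2 uses all later patients.
- Z1 and Z2 are score-type statistics (pooled variance, stratified by invasive ventilation at randomization), because unpooled Wald statistics do not hold 0.025 when the second stage is small.
- State how deaths are counted in the invasive-ventilation endpoints.

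The primary test, and trials that are not enlarged, stay as written. The cost is wording, a little programming and about one point of power for a key secondary. One estimate, assuming survival of 78% vs 85%, is 37.7% falling to 36.6%, still above the 34.5% without an increase. If the SAP already contains such a test, a cross-reference is enough.
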